1. **Describe how and when a subject may withdrawal from the study.** Once the subject completes the first session of the CBT-I, he will not be dropped from the study, unless they specifically request that they not be contacted, or the subject cannot be located for assessment by the 8-week follow-up. The subject may voluntarily withdraw from the study at any point in time. Subjects who are discontinued from the cognitive behavioral therapy intervention will continue to be followed in the study until the completion of the 8 weeks of intervention and the post-study follow-up at 3 and 6 months. The reason the subject is discontinued from the study and any referrals that are made are documented in the appropriate section of the subject's casebooks.
2. **Provide procedures for the orderly termination of participation by the participant and if any consequences would result from early withdrawal from the study.** The subject may be terminated from the research study by the investigator, without regard to his/her consent, under certain conditions. These conditions may include, if s/he does not comply with the recommendations of the research staff, including compliance with study related procedures on ≥3 consecutive office appointments; s/he reports ideas of harm to self or to anybody else with any intent and/or a plan. S/he will additionally be referred to the outpatient treatment program at the Addiction Recovery Unit of the CMCVAMC. Alternatively patient will be withdrawn from the study on successful completion of their study participation.

Subjects will be discontinued/withdrawn from the study if any of the following events occur:

- Any condition which the study psychiatrist finds CBT-I to be a hazard to the subject (i.e. patient seen to be agitated, onset of increasing paranoia, inability to follow through with recommendations and/or homework)
- Participant screens positive at baseline for moderate to severe obstructive sleep apnea (as seen baseline screening portable sleep monitor data), and is currently on not treatment for the obstructive sleep apnea
- Relapse to sustained heavy drinking during treatment as quantified at ≥ 5 standard drinks for men and ≥ 4 standard drinks for women less than 70 years of age, or a total of 14 drinks/ week in men and 7 drinks per week in women for ≥4 days a week and >1 week;

- Development of an inter-current medical illness or condition that requires a new hospital admission

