 - c. Sleep Restriction: As noted above, this behavioral procedure is not without side effects (sleep loss and increases in the daytime symptoms of sleepiness, fatigue, concentration problems, and irritability). The subject will be made aware that "things will [and must] get worse before they get better" and that the transient worsening of symptoms is in the service of long-term gains. This said, in the rare cases where the procedure is viewed by the patient as intolerable, the protocol will be to either 1) re-assess the patient's basal sleep ability (conduct a second baseline assessment) or to substitute sleep compression⁵⁴ for sleep restriction. In addition, similar to our clinical care, we will counsel and monitor subjects at each of the follow-up visits for any excessive daytime drowsiness leading to drowsy driving, a risk factor for a motor vehicle accident, and we will review tips to avoid drowsy driving. If the patient does not wish to engage in these alternatives or the accommodations above do not increase the tolerability of the intervention, then the subject is (as always) free to withdraw from the study.
 - d. Data Collection during Initial Evaluation. Every attempt will be made to minimize the discomfort associated with disclosure of personal data. All of our staff are accustomed to and have a high degree of facility with the acquisition of sensitive information (e.g., drinking history). If, despite our staff's best efforts, the patient is unable to discuss issues that bear on their family and/or clinical history, they are free to not disclose this information and they are free to withdraw from the study. Further, if the patient's reluctance to share information precludes the acquisition of data that are critical to the conduct of the study, they will, at the PI's discretion, be asked to withdraw from the study. In the event that the subject feels they cannot tolerate completing daily sleep diaries or wearing the study actigraph, they will be told that such effects tend to be very transient. If the subject continues to find the collection of such data intolerable and/or is non-compliant, they will initially be assisted by the study-related staff in being compliant with the data collection through frequent reminders (as these data are central to the study). Despite frequent reminders, if they continue to remain non-compliant and at the PI's discretion, they may be asked to withdraw from the study.

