- h. Suicidal/Homicidal Ideation. If the participant reports suicidal ideation with intent to hurt themselves, or if on evaluation, s/he is seen to be a danger to themselves or others, s/he will be referred immediately from the office to the Emergency Department of the CMCVAMC (CMCVAMC -ER). If s/he reports passive suicidal ideation, s/he will be monitored for any change during visits. S/he will also be offered a referral to the Addiction Recovery Unit of the CMCVAMC for further evaluation at the end of the study.

1.3. **If methods of research create potential risks, describe other methods, if any, that were considered and why they will not be used.** In the extreme situation where the risks cannot be mitigated with the above steps, and risk of participation in the study are considered to be greater than non-participation, the P.I. may withdraw the subject from the study and monitor him till the end of the study duration, along with any other additional clinical care that may be warranted.

1.4. **If chart review, breach of confidentiality is always a concern. Specify what steps will be taken to minimize these risks.** These will include the following: restriction of chart review to the P.I. and the study coordinator; storing the identifying information in locked drawers in locked office spaces; use of any of the 17-HIPAAA identifiers to communicate with research staff either over the phone or using the "do not forward" option of the VA email system; and discarding the patient related information into the designated shredding bins within the VA promptly after the information is reviewed or communicated with staff or the specific Veteran.

2. Potential Study Benefits

2.1. **Assess the potential benefits to be gained by the individual subject, as well as benefits that may accrue to society in general as a result of the planned work.** It is possible that the patients will not obtain any benefit from participation in this study. However, it is also possible that some of the participants may have an improvement in their insomnia after completion of their participation in the study. Some potential participants who screen positive for moderate to severe obstructive sleep apnea will be referred to the CMCVAMC Sleep Center for further evaluation and treatment for the

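### Sections S.2 and T.1.2 let a randomized participant be taken out of the study for non-compliance, outside the exceptions in S.1, and no readable text continues ISI, TLFB and SF-12 afterwards

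*Combined protocol and SAP*

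**What the plan says.** **Retention (S.1).** "Once the subject completes the first session of the CBT-I, he will not be dropped from the study", with two exceptions: a request not to be contacted, and failure to locate the participant by the 8-week assessment. S.1 leaves participants free to withdraw voluntarily. It adds that "Subjects who are discontinued from the cognitive behavioral therapy intervention will continue to be followed in the study", through the 8 weeks of treatment and the 3- and 6-month visits.

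**Termination (S.2).** "The subject may be terminated from the research study by the investigator, without regard to his/her consent". One listed condition is "if s/he does not comply with the recommendations of the research staff, including compliance with study related procedures" at three or more consecutive office appointments.

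**Diary and actigraph (T.1.2 item d).** Staff first help and remind the participant, because "these data are central to the study". The text goes on: "Despite frequent reminders, if they continue to remain non-compliant", then at the principal investigator's discretion "they may be asked to withdraw from the study". The item is headed as concerning the initial evaluation. However, the actigraph paragraph in Section N schedules actigraphy, with a diary, at baseline and through the treatment weeks. The matching risk in T.1.1.2 item b is headed as arising during the study.

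**Other follow-up promises.** T.1.3 says that, where risk cannot be mitigated, the principal investigator "may withdraw the subject from the study and monitor him till the end of the study duration". V.3.3 keeps a participant with newly found drug dependence under follow-up until the last study visit.

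**Analysis (V.4.2).** The analysis is by intent to treat, on everyone randomized. The time points of interest are 8 weeks, 3 months and 6 months.

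**The concern.** Intent-to-treat is a rule about collecting data as well as about analysing it. V.4.2 counts every randomized participant, but S.2 and T.1.2 give two routes by which outcome collection can stop by a decision or request of the study team. Staff facing a non-compliant participant cannot tell from the text whether S.1 or S.2 governs. They also cannot tell whether the primary sleep outcome (ISI), the primary alcohol outcome (percentage of days abstinent, from TLFB) and the Aim 3 endpoint (quality of life, from SF-12) should still be sought.

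The reason for removal may not be neutral. T.1.1.2 item b accepts that diaries and actigraphs can transiently worsen insomnia, or be thought to. Those who give up on them could therefore differ in the very outcome being measured. The mixed models and the conditional multiple imputation in V.4.2 limit the damage, but they work from what was recorded and cannot replace outcomes nobody tried to collect.

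**Working it through.** This is mainly a comparison of texts, with a small count at the end.

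**Step 1. Are the compliance reasons among the S.1 exceptions?** S.1 has two exceptions: a no-contact request and not being locatable. Procedural non-compliance (S.2) and diary or actigraph non-compliance (T.1.2 item d) are neither. Both concern leaving the study, not just leaving therapy or stopping one recording.

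**Step 2. Does any follow-up provision reach a compliance removal?**

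| Provision | Whom it covers | Compliance removal? |
|---|---|---|
| S.1 follow-up sentence | Discontinued from the CBT-I intervention | Not as written |
| T.1.3 | Withdrawn because of risk; no instruments named | No |
| V.3.3 | Newly dependent on another drug | No |
| N.2.1.1 to N.2.1.2, phone or mail | Unable to come to the site | Not stated |
| End of S.2, restart clause | Returning to treatment after a short absence or admission | No; concerns restarting, not continued outcome collection |

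No readable text continues ISI, TLFB and SF-12 after a compliance removal.

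**Step 3. Do the rules apply after randomization?** For S.2, yes: its condition needs three consecutive appointments, and the weekly visits follow randomization. For T.1.2 item d the heading points to baseline, but the recordings continue during treatment, so later use is not excluded. The conflict with S.1 stands on S.2 alone.

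**Step 4. What can one removal cost?** V.4.2 counts up to ten follow-up measures. The data collection table lists weeks 1 to 8 and two follow-up visits: 8 + 2 = 10.

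- Removal after week k forgoes 10 − k later measures.
- Earliest use, non-compliance at weeks 1 to 3: 10 − 3 = 7 forgone (weeks 4 to 8, month 3, month 6).
- If the participant misses visits altogether from week 1, session 1 has not been completed and S.1 does not yet protect. If session 1 is completed and weeks 2 to 4 are missed, 10 − 4 = 6 are forgone.
- Latest use within treatment, weeks 6 to 8: 10 − 8 = 2 forgone (months 3 and 6).

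In both early cases, all three time points of interest are lost. The marks in the data collection table are not legible in the available copy, so these are counts of visits. How many times each instrument was due cannot be confirmed.

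**Step 5. Relation to the sample size.** V.4.1 plans 30 per group after 30% missing or dropout: 30 / (1 − 0.30) = 42.9, rounded up to 43 per group, 86 in all. The plan's figure reproduces. It does not split the 30% by reason, so compliance removals may already be inside it.

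**The case against.** The other side has a fair case.

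- **Both rules are permissive.** S.2 and T.1.2 say what may happen. A request to withdraw, made after help and reminders, can presumably be declined. This stands: the plan does not require anyone to be removed.
- **T.1.2 item d may be a baseline tolerability rule.** Its heading supports that, and Q.9.7 defines enrolment as randomization. This weakens the diary and actigraph route without closing it, and leaves S.2 untouched.
- **S.1 may be a default and S.2 its exceptions.** Section S uses discontinuation loosely for both therapy and study, so the sponsor may have meant the follow-up sentence to cover both. That is a plausible intention, but the words limit it to the intervention.
- **The protocol leans towards retention.** V.3.3, the restart clause and the phone or mail option all show this. That makes silence on compliance removals look like an oversight and the remedy easy to accept.
- **Someone who ignores three visits may also ignore the phone.** True, so the yield of the fix is unknown.
- **Not all the text can be read.** Part of the Section N procedures outline and Figure 1 are missing from the available copy. The finding is therefore that no readable text covers the case.

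A reader might infer that these rules bias the comparison towards one arm, because sleep restriction is demanding, or that they reduce power below plan. The documents support neither: they give no removal rate by arm, and the 30% allowance may already include such losses. A reader might also infer that QDT participants are unprotected, because both S.1 sentences name only CBT-I. The text does not settle that, and loose wording is as likely.

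**Conclusion.** The concern holds in a limited form. S.2 permits termination of a randomized participant for procedural non-compliance, and T.1.2 item d permits a request to withdraw for diary or actigraph non-compliance. Neither is an S.1 exception, and no readable text keeps ISI, TLFB and SF-12 going afterwards.

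For one participant, early use loses 6 or 7 of up to 10 follow-up measures and all three time points of interest. Across the trial, the number of removals and the size and direction of any bias are unknown, and no loss of power beyond the planned 30% is claimed. The per-participant count assumes the full weekly schedule and removal at the earliest point S.2 allows.

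The importance of diary and actigraph data, which also feed secondary outcomes, justifies help and reminders. It does not justify stopping the primary outcomes. This is a minor point, worth correcting because the remedy uses procedures the plan already has.

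**What to change.** In S.1, S.2 and T.1.2 item d, state the following:

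- After randomization, in either arm, non-compliance with the diary, the actigraph or other study procedures ends only that recording or the therapy.
- ISI, TLFB and SF-12 continue to 6 months, using the phone or mail route in N.2.1.1 and N.2.1.2 if needed.
- Outcome collection stops only if the participant asks not to be contacted or cannot be located.
- The rules that apply before randomization, and terminations for safety, stay as they are.

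The cost is a few sentences and some additional phone or mail follow-up by existing staff. Sample size, endpoints and the analysis model do not change.

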- Emergence of another substance abuse problem which necessitates inpatient admission or a more aggressive treatment than provided by the protocol.
- Subject is incarcerated for more than a week.

Study participation can be restarted after consultation with the research physician for subjects who 1) return to treatment after a period of brief absence of less than 3 weeks, or 2) return to treatment after brief inpatient hospitalization of less than 2 weeks or additional outpatient treatment. Restarting study procedures is contingent upon clinical need and continuing to meet inclusion and exclusion criteria.

3. **Explain if survival data is required. If so, clarify how data will be obtained.** We will not be assessing for survival data in this pilot study. However we may consider looking at the survival data if there are a significant number of drop out of subjects from the study, with the end point of the survival analysis being the drop out date (i.e. total duration of participation in the study).
4. Not Applicable; subjects not recruited; chart review.

T. Risk/Benefit Assessment

1. Potential Study Risks

- 1.1. Describe and assess all of the following risks that may be associated with the research:
 - 1.1.1. Physical
 - a. Portable Sleep Apnea Monitoring: there may be discomfort associated with the use of nasal cannulas and sensors on the chest/abdomen;
 - b. Overnight Polysomnography: Sleeping in the CMCVAMC sleep laboratory with adhesive leads on the body may be associated with physical discomfort;
 - 1.1.2. Psychological
 - a. Sleep Restriction: patients may experience an increase in the daytime sequelae of insomnia as a result of this intervention (the scheduling of time in bed so as to equal average total sleep time). In the first few days of treatment this is likely to entail some sleep deprivation (~1 hour less sleep than is normal for the individual) and result in a transient increase in daytime sleepiness, fatigue, concentration problems, and irritability;
 - b. Data Collection during the Study: there may be discomfort associated with talking about family history of alcoholism, psychiatric issues and addiction-related issues. Furthermore, in some cases, the use of the sleep diaries and actigraphs may lead to (or be perceived as causing) a transient worsening of insomnia symptoms at home;

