 - c. Relapse to Alcohol: there is a possibility that the transient "side effects" of CBT-I may lead some individuals to resort to occasional alcohol use and that such behavior may also lead to relapse (heavy drinking);
 - d. Use of Other Drugs: there is a possibility that the transient "side effects" of CBT-I may lead some individuals to start using other drugs while taking part in the study-related procedures;
 - e. Suicidal/Homicidal Ideation. While there is no evidence that CBT-I increases suicidal or homicidal ideation, it is a possible consequence of the transient sleep deprivation that occurs with CBT-I. That is, sleep deprivation may lead to decreased inhibition in the frontal brain areas, which may, in turn, lead to a failure to inhibit or cope with such thoughts, especially in vulnerable populations like those who suffer from alcoholism.
 - 1.1.3. Social. A decreased interest in affiliating with other people because of persisting insomnia or a transient increase in the insomnia secondary to the sleep restriction associated with the CBT-I.
 - 1.1.4. Economic. Time spent participating in the study may interfere with the subject's ability to seek employment or participate at his job.

- 1.1.5. Monetary. May be secondary to loss of time spent in participating in the study.
 - 1.1.6. Legal. An increase in the drowsiness may lead to potential risk of a motor vehicle accident.
 - 1.1.7. Loss of confidentiality a. there is a possibility that the subject's identifying data and/or study information may be viewed by non-study personnel.
 - 1.1.8. Assess the likelihood and seriousness of such risks. Although the risks associated with drowsy driving are serious, the likelihood of this risk is low. The likelihood of the other risks are variable, between a low to a moderate level, and specific to the Veteran's individual situation.
 - 1.1.9. Other. N/A
- 1.2. Specify what steps will be taken to minimize these risks.
- a. Portable Sleep Apnea Monitoring: While the use of nasal cannulas and sensors on the stomach and abdomen are required for this screening, subjects that experience discomfort during orientation will be provided (where possible) the opportunity to select from different types of cannulas and sensors .

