 - e. Confidentiality: During the participation in this study, the patient will be assigned a 4-digit unique identification number. This number will not be derived from PHI of any sort (e.g., DOB, SSN, etc.) and will simply represent the study and the subject's recruitment number (e.g., 1001). Study numbers will be linked to subject identifiers in one spreadsheet that will be stored on the PI's password-protected VA online drive. These efforts make it very unlikely that the subject's identifying data and/or study

information may be viewed by non-study personnel. The data will now be captured and stored within the VA Redcap and stored in the secured VA servers.

- f. Relapse to the Drinking. All drinking behavior will be monitored. Monitoring will be based upon self-report items on the daily sleep diaries and clinical interviews by the principal investigator during the outpatient visits. These variables will be monitored for both research and clinical purposes. The research purpose is to determine how alcohol use varies with treatment for insomnia. The clinical purpose is to be able to determine if there has been a resumption of heavy drinking (four standard alcoholic drinks on any day or ≥ 14 drinks a week). If there is a resumption of sustained heavy drinking and this sustained heavy drinking places the subject at risk of medical, psychological or physical harm, then he will be withdrawn from the study, and a referral to the ARU or the inpatient unit, as deemed necessary for further treatment, will be offered to the participant
- g. Use of Other Street Drugs. Patients will be evaluated for the use of other street drugs through structured assessment instruments. Further, if there is a history of regular drug use, the subject will be regularly monitored with standard urine tests (note: this will be a condition for admittance into the study). If regular drug use is detected, the subject will be withdrawn from the study, and a referral to the ARU for further treatment will be offered to the participant.

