- 2.1.1. **Unanticipated problems involving risks to subjects or others.** The unanticipated problems involving risks to the subjects or the others will be notified to the CMCVAMC -IRB. In addition, subjects will be individually notified of the unanticipated problems and the associated risks and benefits of continued participation will be furnished – this will help the Veteran make an informed decision on the need for continued participation.
- 2.1.2. **Interim results.** N/A.
- 2.1.3. **Protocol modifications.** The protocol modifications will be implemented after authorization from the CMCVAMC -IRB. Where ever applicable, the subject will

need to sign an updated consent form, if the changes in the protocol involve him and occur while he is participating in the research study-related procedures.

3. If applicable, define the plan for subjects if research shows results such as:

- 3.1. Depression - depressive symptoms are common in those complaining of insomnia as well in Veterans during early recovery. Depressive symptoms will be monitored through the study.
- 3.2. Suicide - In the unusual situation the participant is seen to develop severe depressive disorder with inability to function with his daily activities or seen to have the onset of suicidal ideation with intent and/or plan, the veteran patient will be referred to the CMCVAMC – ER for further evaluation and treatment.
- 3.3. Abuse – If participant is seen to abuse another drug excluding cannabis and nicotine through the study, s/he will be monitored and at the end of the study, s/he will be recommended a referral back to the ARU. If s/he is currently in treatment in the ARU, her/his treatment team will be notified of the clinical progress in the research study as well as the new substance use. In case the patient is discovered to have dependence to another drug e.g. a sedative-hypnotic or opiates s/he will be monitored through the active study and follow up, educated about her/his drug dependence, urged to abstain from the drug use and if s/he consents, referred to the ARU for active treatment and will also be simultaneously follow up by our research staff, till the end of the study related follow up visits.

4. Statistical Analysis

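### Drug use during the trial triggers study withdrawal in one section and continued follow-up in another, with no rule on later outcome assessments

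*Combined protocol and SAP*

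**What the plan says.** Five parts of the protocol deal with drug use or withdrawal.

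- **Section T, item 1.2.g** is mandatory: "If regular drug use is detected, the subject will be withdrawn from the study", with referral to the Addiction Recovery Unit offered. The preceding sentence sets up surveillance for a subgroup: "if there is a history of regular drug use, the subject will be regularly monitored with standard urine tests". It does not define regular use and does not mention later assessments.
- **Section V, item 3.3** retains the participant: "If participant is seen to abuse another drug excluding cannabis and nicotine through the study, s/he will be monitored", with referral recommended at the end of the study. A participant found to be dependent is followed by research staff through treatment and up to the final follow-up visit.
- **Section S, item 1** says "Once the subject completes the first session of the CBT-I, he will not be dropped from the study", with two exceptions: a request for no contact, and not being locatable by week 8. It adds "Subjects who are discontinued from the cognitive behavioral therapy intervention will continue to be followed in the study", through week 8 and the 3- and 6-month visits.
- **Section S, item 2** lists discontinuation and withdrawal events, including "Emergence of another substance abuse problem which necessitates inpatient admission or a more aggressive treatment than provided by the protocol".
- **Section T, item 1.3** says that in an extreme-risk case "the P.I. may withdraw the subject from the study and monitor him till the end of the study duration".

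Section V, item 4.2 specifies an intention-to-treat analysis of all randomised participants by a linear mixed model, with multiple imputation if missingness is associated with study variables.

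**The concern.** The same participant can be withdrawn under one section and retained under another. If withdrawal is taken to end assessment, the primary outcomes at week 8, 3 and 6 months are lost. The trigger occurs after randomisation and is plausibly related to both sleep and drinking. Section T, item 1.1.2.d also allows that transient effects of CBT-I "may lead some individuals to start using other drugs while taking part in the study-related procedures", so the loss could differ by arm. The protocol gives no rate and no arm difference, so differential loss is possible but not shown.

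Keeping a participant in an intention-to-treat analysis set does not supply outcomes that were never measured. The mixed model and the imputation both work from observed data. They protect only partly if the loss depends on later outcomes that nobody saw.

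**Working it through.** **The rules side by side**

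| Place | Trigger | Consequence | Later outcomes |
|---|---|---|---|
| T 1.2.g | Regular drug use (undefined) | Mandatory study withdrawal | Not mentioned |
| V 3.3 | Abuse of another drug, not cannabis or nicotine | Kept and monitored | No instruments named |
| V 3.3 | Dependence on another drug | Kept, followed to last visit | No instruments named |
| S 2 | Substance problem needing admission or stronger treatment | Discontinued or withdrawn | Not mentioned |
| S 1 | Discontinued from the CBT intervention | Followed to 6 months | Implied; QDT not named |
| T 1.3 | Risk that cannot be mitigated | Optional withdrawal with monitoring | Not mentioned |

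1. *Do T 1.2.g and V 3.3 cover the same people?* Not exactly. T 1.2.g can be read as limited to participants with a drug-use history who are under urine monitoring, and V 3.3 leaves out cannabis and nicotine. They overlap all the same: a urine-monitored participant who develops abuse of, or dependence on, another drug falls under both.
2. *Does severity reconcile them?* No. V 3.3 retains abuse and dependence, which are normally more serious than the regular use that leads to withdrawal in T 1.2.g.
3. *Does Section S settle it?* No. Item 1 has no drug-use exception. Item 2 does allow a substance-related withdrawal, but at a higher threshold than T 1.2.g. The continued-follow-up sentence in item 1 concerns people who stop CBT and does not clearly reach someone withdrawn from the study.
4. *Does T 1.3 settle it?* No. It shows that withdrawal need not end observation, but it is optional and limited to extreme cases.

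**Size, as an illustration**

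Inputs from Section V, item 4.1: 43 per arm; 30% attrition; detectable effect 0.50 SD at 6 months (80% power, intra-class correlation 0.3); SDs of 3.809 for ISI and 15.96 for percentage of abstinent days. The plan's own detectable differences reproduce: 0.50 × 3.809 = 1.90 ISI points and 0.50 × 15.96 = 7.98 percentage points.

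Assumed, because the documents give no figures: k participants lost in one arm, a gap of d SD between their unseen mean and that of the rest of the arm, and no recovery by the model.

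Shift in arm mean = k × d / 43 SD; multiply by the outcome SD for natural units; divide by 0.50 for the share of the detectable effect.

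| k | d | Shift (SD) | ISI points | Abstinent days (percentage points) | Share of detectable effect |
|---|---|---|---|---|---|
| 1 | 0.5 | 0.5/43 = 0.0116 | 0.044 | 0.19 | 2.3% |
| 1 | 1 | 1/43 = 0.0233 | 0.089 | 0.37 | 4.7% |
| 3 | 1 | 3/43 = 0.0698 | 0.266 | 1.11 | 14.0% |

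Planned attrition leaves 43 × 0.70 = 30.1 per arm, a loss of about 13. Losing 1 to 3 participants this way falls within that allowance, so the issue is bias rather than power.

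**The case against.** The strongest case against runs as follows.

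- *Section S is a rule followed by exceptions.* Item 1 states the general rule and item 2 lists departures from it, one of them for substance abuse. This is a fair reading, and it weakens the tension with Section S. The conflict that remains is T 1.2.g against V 3.3.
- *The protocol uses withdrawal and discontinuation loosely.* Withdrawal in T 1.2.g may mean only stopping treatment. That is plausible but not stated, and staff should not have to infer it.
- *Few people are affected.* The exclusion criteria in Section Q, item 2.1.2 remove dependence on other substances and urine screens positive for opioids, cocaine or amphetamine. V 3.3 already keeps contact with dependent participants. This stands, and it is why the likely effect is small.
- *The analysis allows for dropout.* It does, but only from what is observed.
- *The neighbouring item 1.2.f is the stronger case.* It withdraws participants for sustained heavy drinking that puts them at risk of harm, which is tied directly to the Aim 2 outcome. That is true, but it does not remove the problem in item 1.2.g.
- *The change is not free.* Section V, item 2.1.3 requires IRB authorisation and, where applicable, renewed consent. This cost should be counted.

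None of these says which rule governs or requires outcomes after a withdrawal under T 1.2.g.

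**Conclusion.** The concern holds. The protocol contradicts itself on participants who use drugs during the trial, and it leaves outcome collection after a T 1.2.g withdrawal unspecified. The number affected and any difference between arms cannot be estimated from the documents. Under the assumptions above, an arm mean would shift by 0.04 to 0.27 ISI points against a detectable 1.90, or by 0.2 to 1.1 percentage points of abstinent days against 7.98. Those figures assume that the model recovers none of the loss. The bias is therefore probably small. The change is worth making because the contradiction is clear from the text and the remedy costs little, not because a large bias has been shown. Confidence is medium, since the harm depends on how staff read the word withdrawn.

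**What to change.** Amend Section T, item 1.2.g and the substance-use entry in Section S, item 2. Drug use may stop or alter study treatment (CBT-I or QDT) and should prompt referral to the Addiction Recovery Unit, but it should not end study follow-up. Align Section V, item 3.3 with this, so that one rule applies and referral timing agrees. Extend the no-drop and continued-follow-up sentences in Section S, item 1 to both arms. State that ISI, TLFB and SF-12 are collected at week 8, 3 months and 6 months unless the participant refuses contact, by phone or mail where needed; Section N, item 2.1.1 already allows this. Check the heavy-drinking withdrawals in Section T, item 1.2.f and Section S, item 2 at the same time, since they raise the same question.

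The cost is a few sentences of protocol text, IRB authorisation with updated consent where it applies, and a few extra follow-up contacts.
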